4.2.2 Secondary endpoints

SIOPEN numbers of positive lesions will be compared between [¹²⁴I]mIBG PET/CT vs. [¹²³I]mIBG planar scintigraphy+SPECT, using the same methodology and populations as for the primary endpoint.

The primary analysis and the above secondary analysis will be re-analysed using the CURIE score.

Safety and toxicity, are reported using descriptive statistics and line listings only, using the safety population

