15.5 APPENDIX 5: CURIE & SIOPEN SCORING METHODS FOR NEUROBLASTOMA

Figures 2A & 2B:

[figure not shown]

Figure 2A; The Curie method. This method divides the skeleton into nine segments to view osteomedullary involvement and adds a tenth sector that counts any soft tissue involvement to the score. The extension score for this method is graded as: 0. no sites per segment; 1. one site per segment; 2. more than one site per segment; and 3. diffuse involvement (>50% of the segment). The intensity score is graded as: 0. for no uptake; 1. for doubtful uptake; 2. for definite uptake less than liver; and 3. for intense uptake greater than that of liver. Thus, the maximum score for either extension or intensity would be 30. The Curie score has been shown to have a good inter-observer concordance of 92 and 95% in two independent studies. It has been validated in France and is now widely used in North America for the New Approaches to Neuroblastoma Therapy consortium and the Children's Oncology Group (COG).

Figure 2B: The SIOPEN method: the skeletal distribution of *m*IBG is recorded in 12 anatomical body segments as follows: skull, thoracic cage, proximal right upper limb, distal right upper limb, proximal left upper limb, distal left upper limb, spine, pelvis, proximal right lower limb, distal right lower limb, proximal left lower limb and distal left lower limb. The extent and pattern of skeletal *m*IBG involvement is scored using a 0–6 scale to discriminate between focal discrete lesions and patterns of more diffuse infiltration. Each segment is scored as 0. no involvement; 1. one discrete lesion; 2. two discrete lesions; 3. three discrete lesions; 4. > 3 discrete foci or a single diffuse lesion involving < 50% of a bone; 5. diffuse involvement of > 50 to 95% of an entire bone; 6, diffuse involvement of the entire bone, with a maximum score of 72. The SIOPEN score is the current method being used in Europe for a prospective phase 3 neuroblastoma trial.

CANCER RESEARCH UK Statistical Analysis Plan

A Cancer Research UK Phase I/II study to compare $[^{124}\text{I}]m\text{IBG}$ PET/CT to $[^{123}\text{I}]m\text{IBG}$ imaging in patients with metastatic neuroblastoma.

Sponsor protocol number: CRUKD/12/002

EudraCT number: 2012-002029-31

Chief Investigator:

[name]
Nuclear Medicine and PET
Department
Royal Marsden Hospital

[REDACTED]
[REDACTED]
[REDACTED] [REDACTED]
[REDACTED]

Sponsor:

Cancer Research UK
Centre for Drug Development

[REDACTED]
[REDACTED]

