3.1.1 Total number of positive lesions recorded

The total number of lesions will be provided to the Statistician via validated listings from the Sponsor. Data will be recorded in the eCRF by the Trial Manager at the Central Imaging Unit and Source Data Verified (SDV'd) by a Sponsor Clinical Research Associate. The Sponsor Clinical Study Manager will perform a data review before the eCRF is locked and listings are provided to the Statistician.

In summary, the following data will be provided to the Statistician for each evaluable patient for each imaging modality as calculated by each individual Reviewer and as a consensus:

- Number of lesions in each skeletal segment and total number of lesions using the CURIE method (i.e. all lesions with a score of 4 or 5) and also:
 - Total number of lesions with a confidence score of 1
 - Total number of lesions with a confidence score of 2
 - Total number of lesions with a confidence score of 3
 - Total number of lesions with a confidence score of 4
 - Total number of lesions with a confidence score of 5
- Number of lesions in each skeletal segment and total number of lesions using the SIOPEN method (i.e. all lesions with a score of 4 or 5) and also:
 - Total number of lesions with a confidence score of 1
 - Total number of lesions with a confidence score of 2
 - Total number of lesions with a confidence score of 3
 - Total number of lesions with a confidence score of 4
 - Total number of lesions with a confidence score of 5

For example, one Patient's PET/CT scan will have the data above provided but as three or more sets (for detail of the number of reviewers, see the Imaging Review Manual):

- Reviewer 1's data set
- Reviewer 2's data set
- Consensus data set

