3.1.4 CURIE scores

CURIE scores will be recorded using standard scoring methods for each of the 9 defined skeletal areas, and for soft tissue. The CURIE scores will be provided to the Statistician via validated listings from the Sponsor. Data will be recorded in the eCRF by the Trial Manager at the Central Imaging Unit and Source Data Verified (SDV'd) by a Sponsor Clinical Research Associate. The Sponsor Clinical Study Manager will perform a data review before the eCRF is locked and listings are provided to the Statistician.

In summary, the following data will be provided to the Statistician for each patient for each imaging modality as calculated by each individual Reviewer and as a consensus:

- CURIE score

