- Sensitivity/Specificity to be calculated on positive lesions for each imaging modality, [123I]mIBG planar scintigraphy, [123I]mIBG SPECT and [124I]mIBG PET/CT versus the gold standard of the consensus results (from the combined read of [123I]mIBG planar scintigraphy, [123I]mIBG SPECT and [124I]mIBG PET/CT) for all patients and patients with < 20 lesions.

Table 1: Summary of skeletal segments per each imaging modality.

Skeletal Segments		Subject:			
Curie	SIOPEN	[¹²³ I] mIBG Planar	[¹²³ I] mIBG SPECT/CT	[¹²⁴ I] mIBG PET/CT	[REDACTED]
		Vertex to feet	Abdomen & pelvis	Vertex to feet	
Skull & facial bones	Skull & facial bones	✓	x	✓	[REDACTED]
Thorax	Thorax	✓	✓	✓	
Humeri	Humeri L	✓	x	✓	
	Humeri R	✓	x	✓	
Forearms	Forearms L	✓	x	✓	
	Forearms R	✓	x	✓	
Spine C/T (includes Sacrum)	Spine (includes Sacrum)	✓	✓	✓	
Spine L/S (includes Sacrum)		✓	✓	✓	
Pelvis	Pelvis	✓	✓	✓	
Femora	Femora L	✓	x	✓	
	Femora R	✓	x	✓	
Tibiae/fibulae	Tibiae/fibulae L	✓	x	✓	
	Tibiae/fibulae R	✓	x	✓	
Soft Tissue	Soft Tissue	✓	✓	✓	

Authorisation

Author
 
Signature:Date:
 
Name & Position: [REDACTED]

Peer Reviewer
 
Signature:Date:
 
Name & Position: [REDACTED]

Approval
 
Signature: Date:
 
Name & Position: [name] (CI)

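### SAP 4.2.2 names the Curie score where the binomial method needs Curie-method lesion counts, and Addendum Table 1 puts the sacrum in two Curie spine segments

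*Combined protocol and SAP*

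**What the plan says.** SAP 4.2.1 defines, for each patient, n123 and n124 as the numbers of lesions called positive by consensus (confidence 4 or 5) on planar scintigraphy and on PET/CT. The smaller of the two is n_min. The endpoint is the sum of n_min over the sum of n123, and success is judged by an exact one-sided binomial test against 90% at 0.025. The counts are those made by the SIOPEN method.

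SAP 4.2.2 carries the same method over to planar plus SPECT, again on SIOPEN numbers of lesions, and then states: "The primary analysis and the above secondary analysis will be re-analysed using the CURIE score".

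Elsewhere the SAP treats Curie counts and Curie scores as two different data items:

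- SAP 3.1.1 supplies the "Number of lesions in each skeletal segment and total number of lesions using the CURIE method", restricted to confidence 4 or 5.
- SAP 3.1.4 lists the score as its own item: "CURIE scores will be recorded using standard scoring methods for each of the 9 defined skeletal areas, and for soft tissue".
- Protocol Appendix 5 describes the extension scale as "graded as: 0. no sites per segment; 1. one site per segment; 2. more than one site per segment", with grade 3 for diffuse disease. It gives a second 0-3 scale for intensity and a maximum of 30 on either scale.

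The later SAP addendum moves the primary and SPECT comparisons to a per-segment basis defined by its Table 1, repeats them for soft tissue, and reports SIOPEN and Curie scores descriptively. It does not mention the re-analysis sentence in 4.2.2. In Table 1 the Curie column has two spine rows, "Spine C/T (includes Sacrum" and "Spine L/S (includes Sacrum" (closing brackets omitted here). The SIOPEN column has one spine row, which also includes the sacrum.

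**The concern.** A binomial test needs units that are each detected or missed. Above one site, the Curie extension grade stops counting: grade 2 covers two sites or twenty. Grade 3 describes diffuse spread and not three of anything. The intensity grade carries no count at all, and 4.2.2 does not say which scale would be used. A statistician who takes 4.2.2 at its word would draw on the score listing when the count listing is the one that fits the method. The result could show agreement where lesions were missed, or a shortfall where none were.

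The Table 1 label is a separate matter. Once the analysis is per segment, the segments must not overlap. With the sacrum in both Curie spine rows and no allocation rule, a sacral lesion could be entered twice. It could also be placed in one row for planar and in the other for PET/CT.

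**Working it through.** **1. The plan's own design figures, which are for lesion counts.** Inputs from protocol 12.1 and SAP 1.4: stage 1 has 50 lesions, with futility at 45 or fewer and efficacy at 50; the final stage has 100 lesions, with success at 96 or more; p0=0.90 and p1=0.97. With X1 and X2 each binomial(50, P):

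P(success) = P(X1=50) + sum over x=46 to 49 of P(X1=x) × P(X2 ≥ 96−x).

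| Quantity | Computed | Stated |
|---|---|---|
| Power at 97% | 0.8215 | 82% |
| Alpha at 90% | 0.0266 | 0.03 |
| Efficacy stop at 97% | 0.218 | 22% |
| Futility stop at 90% | 0.569 | 57% |

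The stated figures reproduce. They apply to lesion counts, and the plan gives no such figures for a Curie score.

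**2. Score against count in one segment (hypothetical, extension scale from Appendix 5).**

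- Planar 6 discrete sites, PET/CT 2. Counts: min(6,2)/6 = 2/6 = 33%. Scores: both are grade 2, so min(2,2)/2 = 100%.
- Planar diffuse (grade 3), PET/CT resolving the same disease into discrete sites (grade 2). Scores: min(3,2)/3 = 67%, although no disease was missed.

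**3. Effect on the test (assumed data).** Take 10 patients, each with 2 involved segments of 5 discrete planar lesions and no diffuse disease. PET/CT finds 4 of 5 in each segment.

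- Counts: planar 10×2×5 = 100, matched 10×2×4 = 80. P(X ≥ 80 | 100, 0.90) = 0.999, nowhere near rejecting the null.
- Extension scores: planar 10×2×2 = 40, matched 40. P(X=40 | 40, 0.90) = 0.90^40 = 0.015, below 0.025.

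The same scans fail on counts and pass on scores.

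**4. The sacrum in the per-segment analysis.**

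- *Different placement.* One sacral lesion is seen on both scans, with planar placing it in C/T and PET/CT in L/S. In the C/T row n123=1 and n124=0, giving 0/1; in the L/S row n123=0. By patient total the same lesion is 1/1. The segment table would record a miss that did not occur.
- *Double entry.* The number of sacral lesions is not in the documents, so a range is shown. The figures also assume that segments are summed, which no section states.

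| Assumed data | Without doubling | With doubling |
|---|---|---|
| 10 concordant sacral lesions | 95/100, p=0.058 | 105/110, p=0.031 |
| 15 concordant sacral lesions | 95/100, p=0.058 | 110/115, p=0.022 |
| 20 concordant sacral lesions | 95/100, p=0.058 | 115/120, p=0.016 |
| 1 missed sacral lesion | 96/100, p=0.024 | 96/101, p=0.054 |

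On those assumptions, double entry could move the result across 0.025 in either direction.

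**The case against.** The best defence is that the intended reading can be recovered. SAP 3.1.1 supplies SIOPEN and Curie lesion counts in parallel under one positivity rule, and that rule matches the definition of n123 and n124 in 4.2.1. Repeating the primary analysis by Curie then most naturally means running the same test on the parallel count. The addendum reports the scores descriptively, which fits that reading, and the C/T label looks like a copying slip.

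Much of this stands. A reader might infer that the Curie re-analysis has no valid unit at all; 3.1.1 shows that it has one. A reader might also infer that soft tissue is tested mainly through this re-analysis. The addendum repeats both comparisons separately for soft tissue, and Table 1 has a soft-tissue row under both methods. Nor does any section order sacral lesions to be counted twice or segments to be pooled; 3.1.1 supplies the patient total as an item of its own.

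The defence does not remove the point. SAP 4.2.2 speaks of numbers of lesions in one sentence and of a score in the next, and the SAP uses those words for different listings. SAP 4.1 makes between-modality agreement descriptive unless a later section says otherwise, and 4.2.2 is such a section. The addendum leaves its sentence in force. The Table 1 overlap is printed in the table that defines the segments.

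**Conclusion.** SAP 4.2.2 names the wrong unit for the Curie re-analysis. Read literally, it puts ordinal grades into a test for counts and can reverse the conclusion, as 80/100 against 40/40 shows. Those data are invented to show the mechanism; they use the extension scale only and assume no diffuse disease, and they do not predict this trial's results. Separately, Table 1 leaves a sacral lesion without a unique Curie segment. The size of that effect cannot be determined from the documents.

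The reach is limited. The primary test rests on SIOPEN counts, and the SIOPEN column has a single spine row. No stopping rule, sample size or success criterion depends on the Curie re-analysis. The documents do not support reading this as a flaw in the primary result. It is a correction that should be made to a supporting analysis.

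**What to change.** 1. In SAP 4.2.2, replace the reference to the Curie score with Curie-method lesion counts (SAP 3.1.1, confidence 4 or 5).
2. Keep the Curie scores descriptive, as the addendum states, and say that they do not enter the binomial test.
3. In Addendum Table 1, assign the sacrum to one Curie spine row only. The L/S row is the evident candidate, for the sponsor to confirm. Add a rule that each lesion belongs to one segment and that the same allocation holds for every modality.
4. The addendum followed a review of a statistical report, so if the Curie re-analysis has already been run, state which listing was used and how sacral lesions were allocated.

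The first three are wording changes. The counts are already among the data items due to the statistician, so no new reading or data collection is needed. If sacral lesions were entered in both rows or allocated differently between modalities, those entries would need to be checked.

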4.2.3 Tertiary endpoints

4.2.3.1

[REDACTED]

[REDACTED]

[REDACTED]

[REDACTED]

4.2.3.2

[REDACTED]

[REDACTED]

[REDACTED]

4.2.3.3 [REDACTED]

[REDACTED]

4.2.3.4 [REDACTED]

[REDACTED]

4.2.3.5 [REDACTED]

[REDACTED]

4.2.3.6

[REDACTED]

5 Interim Analyses

The interim analysis should be performed at the first available timepoint after no less than 9 evaluable patients have completed both their [¹²³I]mIBG and [¹²⁴I]mIBG scans, and a combined total of at least 50 lesions have been found on [¹²³I]mIBG. At this point the consensus panel should meet to evaluate and record their opinions as soon as practically possible. Once this has been done, the interim analysis can be performed.

Initially an exact one-sided binomial test of the null hypothesis: $p \geq 97\%$ will be done using $\alpha = 0.05$. If this is rejected in favour of the alternative hypothesis $p < 97\%$, the study will be stopped early for futility.

If the null hypothesis is accepted, a further one-sided binomial test of the null hypothesis, $p \leq 90\%$, will be done using $\alpha = 0.025$. If this is rejected in favour of the alternative hypothesis $p > 90\%$ then the trial may be stopped early for efficacy. If this null hypothesis is not rejected, the trial will continue recruitment to the second and final stage.

The results of the interim analysis should be reported to the trial sponsor.

6 Timing of Statistical Analysis

The interim analysis will be performed as detailed in section 5. The final analysis should be performed after all patients recruited to the trial have undergone all scheduled on-trial scans,

7 Data checking plan

All data checking activities will be carried out by the study sponsor before transferring data for analysis. On receipt of data by the study statistician no further formal data checks will be made.

8 Signatures

Study Statistician

_____ Date _____
[REDACTED]

Chief Investigator

_____ Date _____
[name]

ADDENDUM

CCR4051 124ImIBG: Statistical Analysis Plan

Following the statistical report review on 9th November 2020 by the internal and external mIBG Project Team, this addendum has been written to clarify the analysis of the mIBG trial endpoints.

Primary objective	Endpoint	Change in analysis with rationale
1. To show that [¹²⁴ I]mIBG PET/CT can detect an equal or greater number of neuroblastoma lesions compared to conventional [¹²³ I]mIBG planar scintigraphy.	1. Comparison of the percentage of lesions detected as positive by [¹²³ I]mIBG planar scintigraphy which are also considered positive with [¹²⁴ I]mIBG PET/CT.	Analysis will be done per skeletal segment as defined in table 1 below. This is because each imaging modality covers specific skeletal areas. Again, this analysis will be repeated separately for soft tissue segment.

Secondary objectives	Endpoints	Change in analysis with rationale
1. To show that [¹²⁴ I]mIBG PET/CT can detect an equal or greater number of neuroblastoma lesions compared to conventional [¹²³ I]mIBG scintigraphy with 3D imaging by SPECT (single photon emission computerised tomography).	1. Comparison of the percentage of lesions detected as positive by [¹²³ I]mIBG SPECT which are also considered positive with [¹²⁴ I]mIBG PET/CT.	Analysis will be done per skeletal segment as defined in table 1 below. This is because each imaging modality covers specific skeletal areas. Again, this analysis will be repeated separately for soft tissue segment.
2. Assessing the safety and toxicity profile of a single intravenous administration of [¹²⁴ I]mIBG.	2. Determining the causality of each adverse event to [¹²⁴ I]mIBG and grading severity according to National Cancer Institute Common Toxicity Criteria for Adverse Events (NCI CTCAE) version 4.02.	N/A

Tertiary objectives	Endpoints	Change in analysis with rationale
[REDACTED]	[REDACTED]	[REDACTED]
[REDACTED]	[REDACTED]	[REDACTED]
[REDACTED]	[REDACTED]	[REDACTED]
[REDACTED]	[REDACTED]	[REDACTED]
[REDACTED]	[REDACTED]	[REDACTED]

Tertiary objectives	Endpoints	Change in analysis with rationale

	

	

Others:

- Summary of SIOPEN & CURIE scores will be reported descriptively as mean, SD, median, IQR and ranges.
- Sensitivity/Specificity to be calculated on positive lesions for each imaging modality, [123I]mIBG planar scintigraphy, [123I]mIBG SPECT and [124I]mIBG PET/CT versus the gold standard of the consensus results (from the combined read of [123I]mIBG planar scintigraphy, [123I]mIBG SPECT and [124I]mIBG PET/CT) for all patients and patients with < 20 lesions.

Table 1: Summary of skeletal segments per each imaging modality.

Skeletal Segments		Subject:			
Curie	SIOPEN	[¹²³ I] mIBG Planar	[¹²³ I] mIBG SPECT/CT	[¹²⁴ I] mIBG PET/CT	[REDACTED]
		Vertex to feet	Abdomen & pelvis	Vertex to feet	
Skull & facial bones	Skull & facial bones	✓	x	✓	[REDACTED]
Thorax	Thorax	✓	✓	✓	
Humeri	Humeri L	✓	x	✓	
	Humeri R	✓	x	✓	
Forearms	Forearms L	✓	x	✓	
	Forearms R	✓	x	✓	
Spine C/T (includes Sacrum)	Spine (includes Sacrum)	✓	✓	✓	
Spine L/S (includes Sacrum)		✓	✓	✓	
Pelvis	Pelvis	✓	✓	✓	
Femora	Femora L	✓	x	✓	
	Femora R	✓	x	✓	
Tibiae/fibulae	Tibiae/fibulae L	✓	x	✓	
	Tibiae/fibulae R	✓	x	✓	
Soft Tissue	Soft Tissue	✓	✓	✓	

Authorisation

Author
 
Signature:Date:
 
Name & Position: [REDACTED]

Peer Reviewer
 
Signature:Date:
 
Name & Position: [REDACTED]

Approval
 
Signature: Date:
 
Name & Position: [name] (CI)

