Radioiodine therapy with [¹³¹I]mIBG is increasingly a component of trials for high risk neuroblastoma and recent evidence has shown that individualised treatment planning based on absorbed whole-body and tumour doses can be performed to prevent under-treatment or unnecessary toxicity from over-treatment (Gaze, Chang et al. 2005, Buckley, Chittenden et al. 2009). The increased spatial resolution of three dimensional [¹²⁴I]mIBG PET/CT imaging over 3D [¹²³I]mIBG SPECT would improve the accuracy of quantitative imaging on which patient-specific absorbed dose calculations are based.

In summary, the hypothesis of this study is that [¹²⁴I]mIBG PET/CT will achieve high sensitivity and specificity in detecting neuroblastoma tumour, deliver the excellent spatial resolution required to precisely localise small disease foci, offer reliable and reproducible quantitative assessment of disease extent, and enable better evaluation of disease response to existing and new therapies for neuroblastoma. In the future it could provide more functional and anatomical data than routine [¹²³I]mIBG scintigraphy, where full body planar scintigraphy is performed alone or combined with 3D SPECT scintigraphy of the thorax and abdomen, and conventional cross sectional CT or MRI scanning. This would minimise the need to perform two or more scans of different modality.

2.6.1 [REDACTED]

[REDACTED]

[REDACTED]

2.6.2

[REDACTED]

[REDACTED]

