9 ASSESSMENT OF IMAGING TECHNIQUES

9.1 PRIMARY ANALYSIS

Analysis of [¹²⁴I]mIBG PET/CT and [¹²³I]mIBG planar scintigraphy will be performed retrospectively by an agreed number of observers who are experienced in the assessment of neuroblastoma. The observers will perform the analysis separately from each other and will be blinded from the scores of the other observers. An observer will perform their review of each modality for a patient several weeks apart. [¹²³I]mIBG imaging and [¹²⁴I]mIBG PET/CT imaging will be reviewed on a Hermes workstation (Hermes Medical Solutions, Sweden). Observers may perform their assessment of study imaging data in batches throughout the study but will not share their scores until the conditions are met to trigger the interim and final analyses as described in section 12.2.

For each modality, suspected lesions will be judged positive, negative, or equivocal with regard to neuroblastoma involvement by each observer. A final determination of each lesion as positive, negative or equivocal will be established through consensus between all observers:

- Positive – all reviewers consider it positive
- Negative – all reviewers consider it negative
- Equivocal – fewer than all reviewers can agree on whether the lesion is positive or negative

The scores for each modality will be submitted to the statistician at the interim and final analyses to meet the primary endpoint. The percentage of positive findings identified on routine [¹²³I]mIBG planar scintigraphy also identified by the novel [¹²⁴I]mIBG PET/CT will be determined. Recruitment will cease during the interim analysis.

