3.1.2 Confidence scores

For each lesion (or for each SIOPEN area in which diffuse disease is noted), the observer (or group of observers for the consensus opinion) will also note a confidence score to measure their certainty of the lesion being malignant, on a 5 point scale from 1 (negative) to 5 (definitively positive). See section 3.1.1 detailing how this data will be provided to the Statistician.

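### Specificity is planned on positive lesions, a set with no reference-negative units; define it on the segments each modality covers, or drop it

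*Combined protocol and SAP*

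**What the plan says.** The last bullet under Others in the SAP addendum plans "Sensitivity/Specificity to be calculated on positive lesions for each imaging modality", judged "versus the gold standard of the consensus results (from the combined read of" planar scintigraphy, SPECT and PET/CT). It is to be done "for all patients and patients with < 20 lesions". The bullet does not say what counts as a negative unit.

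Three other places bear on this.

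- **What readers score.** Protocol 9.1 says that "suspected lesions will be judged positive, negative, or equivocal with regard to neuroblastoma involvement by each observer". SAP 3.1.2 adds a five-point confidence score per lesion, or per SIOPEN area where disease is diffuse; 1 means negative. No fixed list of sites is set at lesion level.
- **What the statistician receives.** SAP 3.1.1 lists, for each modality, by reviewer and as a consensus, the "Number of lesions in each skeletal segment and total number of lesions using the SIOPEN method" (scores 4 or 5), and totals by score, such as "Total number of lesions with a confidence score of 1". These are counts. The legible text mentions no matching of lesions between reads.
- **Where segments are already the unit.** The addendum moves the primary and the first secondary comparison to a per-segment analysis because coverage differs by modality. It does not say this for sensitivity and specificity.

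The protocol rationale (2.6) expects that PET/CT "will achieve high sensitivity and specificity in detecting neuroblastoma tumour", among other aims.

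**The concern.** Specificity is the share of reference-negative units that the test also calls negative. A set of lesions chosen for being positive has no unit that is negative on both test and reference, so the quantity named in the bullet does not exist on that set. Bringing in the low-scored spots gives a number, but its denominator is whatever the readers chose to write down. Two equally good readers, one who notes every doubtful spot and one who does not, would report different specificities from the same images.

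In the visible text this is the only plan to estimate specificity. The primary measure in SAP 4.2.1 does not replace it: it divides the summed per-patient minimum of the two lesion counts by the summed planar count, so extra PET/CT foci never lower it. A meaningless specificity would therefore be the only reported evidence on false positives. The addendum also says it was written after a statistical report had been reviewed, so an undefined denominator leaves a choice to be made once data have been seen.

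**Working it through.** The documents give no specificity value, target or sample size, so there is no planned figure to reproduce. The check is to apply the definition to each way the bullet can be read.

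**Formula.** Specificity = TN / (TN + FP), where TN and FP are the reference-negative units called negative and positive by the modality. Sensitivity = TP / (TP + FN).

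**Reading 1: lesions positive on the reference.** TN = 0 and FP = 0, so specificity = 0/0, undefined.

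**Reading 2: lesions positive on the modality or on the reference.** TN = 0. Specificity = 0/FP = 0% if FP > 0, and 0/0 if FP = 0.

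**Reading 3: recorded negative spots added.** Assume TP = 90, FN = 10 and FP = 5 (illustrative; not in the documents), with k listed true negatives. Specificity = k/(k + 5):

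| k | Specificity | Sensitivity |
|---|---|---|
| 0 | 0/5 = 0% | 90% |
| 5 | 5/10 = 50% | 90% |
| 10 | 10/15 = 67% | 90% |
| 50 | 50/55 = 91% | 90% |
| 95 | 95/100 = 95% | 90% |

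Sensitivity, 90/(90 + 10), is not affected by missing negatives. It still requires each lesion to be matched to the reference.

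**Segment as the unit.** The denominator is then fixed by the grid. Table 1 of the addendum lists 12 SIOPEN skeletal segments, all ticked for planar and PET/CT. For SPECT only thorax, spine and pelvis are ticked. With the minimum of 9 or 33 evaluable patients:

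- planar and PET/CT: 12 × 9 = 108, or 12 × 33 = 396;
- SPECT: 3 × 9 = 27, or 3 × 33 = 99. These are maxima, since the protocol expects SPECT only in the majority of patients.

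Assumed example: 9 patients, 108 segments, 5 false-positive segments. Clopper-Pearson intervals, ignoring clustering within patient:

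| Segments diseased | Specificity | 95% CI |
|---|---|---|
| 25% | 76/81 = 93.8% | 86.2 to 98.0 |
| 50% | 49/54 = 90.7% | 79.7 to 96.9 |
| 75% | 22/27 = 81.5% | 61.9 to 93.7 |

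**Effect of the reference.** The reference is a joint read of the three tests being judged. If it is positive whenever any test is positive, every reference-negative segment is negative on all three, so FP = 0 and specificity = 100% for each, whatever the truth. A simulation illustrates this (assumed: 40% of segments diseased; sensitivities 0.80, 0.85 and 0.95 for planar, SPECT and PET/CT; the same true specificity for all; independent errors; all segments covered):

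| True specificity | Any-positive reference | Two-of-three reference |
|---|---|---|
| 95% | 100% for all | 93.8 to 95.2% |
| 90% | 100% for all | 90.0 to 91.6% |
| 85% | 100% for all | 86.7 to 88.6% |

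Under the two-of-three rule eight of the nine values lie above the truth; the exception is PET/CT at a true 95% (93.8%). The usual direction is upward.

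**The case against.** The strongest reply is that the phrase about positive lesions may name the positivity threshold (score 4 or 5) and not the sample. Negative spots are recorded, the tertiary text is redacted, and the imaging review manual is not available. So the documents do not prove that the analysis will use positives only. That stands, but it does not rescue the bullet: if listed spots are the unit, Reading 3 applies. Nor can segments be assumed, since the bullet speaks of lesions and subsets patients by lesion count.

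A reader might infer more than the documents support:

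- *That the delivered segment data would give a valid specificity.* They make one computable for each modality. The reference includes the index tests, and the joint three-modality read is not named in the legible data list. It may sit in unreadable text, so its absence cannot be asserted either.
- *That 108 or 396 units apply throughout.* They do not for SPECT. Unscanned segments entered as zero lesions would count as true negatives when the reference is negative and as misses when it is positive.
- *That lesion-level sensitivity and false-positive foci can be reported anyway.* Both need the matching that counts do not provide.
- *That specificity is half of the study's hypothesis.* Protocol 2.6 also lists spatial resolution, quantification and response evaluation, and no visible primary or secondary objective names specificity.

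**Conclusion.** The point holds as a defect in a descriptive analysis. Specificity on positive lesions is undefined, or 0% with any false positive; with listed negatives added it can lie anywhere from 0% to 95% for identical images, assuming 5 false positives and 0 to 95 listed negatives. The algebra rests on the definition alone; those counts are illustrative.

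A segment-level figure has a fixed denominator but remains limited by a reference that contains the tests, by partial SPECT coverage and by clustering within patients. A reader might infer that the trial's conclusion is at risk. It is not: the bullet carries no test, target or stopping role, and the primary analysis does not use it. What is at stake is the accuracy figure that would be reported.

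**What to change.** Replace the bullet with a segment-level analysis:

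1. A segment is positive if it has at least one lesion (or a diffuse area, scored under SAP 3.1.2) with confidence 4 or 5, and negative otherwise. Apply the same rule to the reference.
2. For each modality, include only patients scanned with it and only the segments Table 1 ticks for it. First confirm the SPECT ticks: the table heads that column abdomen and pelvis but ticks thorax, while the protocol describes chest and abdomen.
3. Analyse soft tissue separately, after checking that it is recorded in the same form, since SAP 3.1.1 names skeletal segments only.
4. Give sensitivity and specificity with 95% confidence intervals that allow for clustering within patient.
5. Confirm that the joint three-modality read is recorded per segment. If it is not, drop specificity.
6. State that the reference includes the index tests, that specificity therefore tends to be too high, and that it is 100% by construction if any positive modality makes the reference positive. Say how the joint read reaches its call.
7. Report lesion-level sensitivity or false-positive foci per patient only if lesions are matched to the reference.

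**Cost.** A short SAP paragraph and one data check. Per-segment positive counts by modality are already listed for transfer; if the joint read was not recorded per segment, the cost is losing specificity. The downside is that a segment with several lesions counts once, so segment sensitivity will tend to exceed lesion sensitivity.
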